## 1. Title

# **Laparoscopic versus open ablation of liver malignancies: a randomized, controlled multicenter trial**

## 2. Aims

We will conduct a randomized study to compare laparoscopic ablation for liver tumors with the standard care (open ablation) with the hypothesis to reduce complications and maintain similar treatment success rate. We will

- Investigate differences in complications (primary outcome), length of hospital stay and mortality between laparoscopic and open ablation.
- Investigate differences in success rate (complete ablation response) between laparoscopic and open ablation.
- Investigate differences in quality of life between laparoscopic ablation and open ablation and explore how patients with liver tumors experience ablation of a liver tumor.

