## Endpoints and outcome measurement

### Primary outcome

- Treatment-related complications that develop within 30 days following ablation will be reported according to the Clavien-Dindo Classification, which is considered the best validated classification to rate surgical complications. The primary outcome is defined as any complication (Grade 2 or above) in the Clavien-Dindo Classification.

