### Secondary outcomes

- Success rate of the procedure is described as rate of complete ablations one month after procedure. A complete ablation response is defined as complete absence of enhancing tissue at the tumor site after one month on CT-scan.
- Complications reported as Comprehensive Complication Index (CCI). CCI is a scoring system for overall morbidity and is reflected on a scale from 0 (no complication) to 100 (death). It is based on Clavien-Dindo classification and takes all complications after a procedure into account.
- Highest complication grade according to the Clavien-Dindo Classification
- Wound infections within 30 days is defined as wound dehiscence requiring secondary suturing or treated conservatively. Fascial dehiscence will be recorded separately.

- Postoperative liver failure is defined by the “50-50 criteria” (prothrombin time <50% and serum bilirubin >50 µmol/L on postoperative day five).
- Postoperative pain will be assessed by Visual Analogue Scale for acute and chronic pain, pre-operatively and on each post-operative day until discharge, after seven days, 14 days and one month.
- Overall and disease-free survival.
- Procedure related mortality within 90 days.
- HRQoL before and one month after the procedure will be assessed using the Danish version of The European Organization for Research and Treatment of Cancer Quality of Life (EORTC QLQ C30) and a disease specific form for patients with HCC (QLQ HCC18), cholangio carcinoma (QLQ BIL21) or colorectal liver metastases (QLQ LM21). Depression and anxiety will be assessed before and one month after procedure using PHQ-9 and GAD-7, respectively. Recovery will be assessed with the Quality of recovery (QoR-15) before and seven days after the procedure.
- Length of hospital stay defined as time in days from operation to discharge.
- Blood loss during surgery
- Need for perioperative blood transfusion
- Conversion rate in the laparoscopic group
- Duration of procedure
- Model for Endstage Liver Disease (MELD) and Child-Pugh score before operation and on postoperative day five.
- Patients experiences of undergoing ablation will be explored by individual interviews one months after the procedure.

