##### Sample size

Based on a previous study from our center, the primary outcome (any complication Grade 2 or above, Clavien-Dindo Classification) occurred in 45% of patients undergoing open ablation. The similar complication rate from another external study was 39.5%. The hypothesis is that with a laparoscopic approach, the complication rate can be reduced to 10%. With an alpha of 5% and power of 80%, we will need 60 patients (30 in each arm).

The rate of complete ablation in one month is approximately 95% for open ablations. Using a non-inferior approach and assuming a similar rate of complete ablation in the laparoscopic group, we will need 54 patients (non-inferiority limit 15%, alpha 5% and power 80%).

By including 80 patients, both above sample-size calculations will be covered, and we will have sufficient material compensate for possible excluded patients. Before randomization, we will perform training of laparoscopic ablation using a training fantom developed for the purpose. Accuracy of laparoscopic needle placement with ultrasonography will be assessed using a gel with artificial tumors and an artificial abdominal wall. In addition, we will perform 20 cases with laparoscopic ablation to ensure that technique and learning curve is sufficient compared with our standard of care (open ablation). At this point, sufficient safety and efficacy (comparable to the literature) will be

ensured prior to randomization and additional cases and additional training may be performed is necessary.

After randomization of the first 15 laparoscopic cases, we will perform an interim analysis looking only at conversion rates in the laparoscopic group due to lack of feasibility. In case of a conversion rate above 20%, sample size will be increased according to the conversion rate, e.g. 20% more patients in each group with a conversion rate of 20%. This is done to ensure sufficient power in our comparison between the open and laparoscopic technique.

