## 14. Ethical considerations

Currently, ablation during open surgery is the standard of care for tumors not amenable for percutaneous ablation. Compared with laparoscopic technique, open surgery is associated with higher risk of complications and post-operative pain. However, currently there is insufficient evidence to use laparoscopic ablation of liver tumors as the standard of care. The current study has the potential to provide this evidence.

Laparoscopic ablation is less invasive including small incisions with assumed less pain and risk of postoperative ablation. All side effects should be less severe compared with standard of care. The main possible disadvantage for the patients would be if laparoscopic ablation had less treatment success rate compared with open due to limitation in tumor visualization with ultra-sound or placement of ablation needle in the tumour. If the success rate was lower, this may entail a subsequent procedure to ensure sufficient ablation of the tumor. However, previous reports suggest a similar success rate for laparoscopic ablation compared with open. Thus, we consider this risk to be minimal. Even so, we consider that lower complication would outweigh the risk of a subsequent treatment. Moreover, if success rate was initially lower in the laparoscopic group, this

would likely improve with more experience with the technique among the surgeons. Thus, included patients as well as future patients will likely receive terapeutical benefit with the study.

The study will be conducted in accordance with the principles of the Helsinki Declaration.

Approval will be obtained from the local Scientific Ethics Committees and the Data Protection Authority before the start of the study. The investigator responsible for the study will also inform the Scientific Ethics Committee of significant or major changes in the protocol, and the study will be conducted in accordance with current regulations for clinical studies on humans. All patients participating in the study must provide oral and written informed consent before being included in the study. The patients are informed that the consent includes obtaining relevant medical record information related to their current admission, as well as that this information will be submitted upon inspection by relevant authorities.

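### The two-part claim (fewer complications, success maintained) is not tied to testing and meeting the plan's own 15-point limit on complete ablation

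*Combined protocol and SAP*

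**What the plan says.** Section 2 (Aims) joins two statements in one hypothesis: the trial compares laparoscopic with open ablation "with the hypothesis to reduce complications and maintain similar treatment success rate".

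The outcome sections separate them. Under Primary outcome: "The primary outcome is defined as any complication (Grade 2 or above) in the Clavien-Dindo Classification". Complete ablation comes first in the list under Secondary outcomes: "Success rate of the procedure is described as rate of complete ablations one month after procedure".

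The Sample size section treats both as planning targets:

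- **Complications.** The event "occurred in 45% of patients undergoing open ablation", and the hypothesis is that with laparoscopy "the complication rate can be reduced to 10" per cent. This gives 60 patients at alpha 5% and power 80%. An external control rate of 39.5% is also cited.
- **Success.** This is planned as non-inferiority, with 95% in both arms, a limit of 15 points, alpha 5% and power 80%, giving 54 patients.
- **Both.** "By including 80 patients, both above sample-size calculations will be covered".

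Section 4 (Statistical considerations) assigns Fisher's exact test at p < 0.05 to the primary outcome and to every dichotomous secondary outcome, in intention-to-treat and per-protocol analyses. It mentions no non-inferiority test, no confidence bound and no rule for reading the two results together. The 15-point limit appears only in the Sample size section.

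**The concern.** The plan names a limit for loss of ablation success and sizes the trial against it, but the analysis never uses it. A difference test answers another question: a non-significant Fisher result does not show that success is maintained, least of all with 40 patients per arm. Since no section says what must be shown before both halves of the hypothesis are claimed, a significant result on complications beside a non-significant one on success could be read as confirming the whole hypothesis.

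The stakes are set by the protocol itself. Sections 6 and 14 name lower success as the main possible disadvantage of laparoscopy. Section 14 also says that the study could supply the evidence now lacking for laparoscopic ablation as standard of care. That use needs both halves.

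**Working it through.** **Inputs from the Sample size and Method sections.** Complications 45% (open) v 10% (laparoscopic), alternative control rate 39.5%; success 95% v 95%; limit 15 points; 40 per arm. The true success of 80% used below is an assumption: 95% minus the plan's own limit.

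**1. Reproduce the plan's sample sizes.**

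- Complications, two-sided 5%, power 80%: n = [1.960·√(2·0.275·0.725) + 0.842·√(0.45·0.55 + 0.10·0.90)]² / 0.35² = 24.3. With continuity correction, (24.3/4)·[1 + √(1 + 4/(24.3·0.35))]² = 29.8, so 30 per arm and 60 in total, as stated.
- Success, one-sided 5%: n = (1.645 + 0.842)²·2·0.95·0.05 / 0.15² = 26.1, so 27 per arm and 54 in total, as stated. At one-sided 2.5% it would be 34 per arm, or 68. The plan's 54 therefore implies one-sided 5%, although the sidedness is not stated.

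**2. The analysis as written, 40 per arm (exact binomial enumeration of two-sided Fisher, p < 0.05).**

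- Complications 45% v 10%: power 0.935. This does not depend on the success rates. With 39.5% v 10% it is 0.841.
- Success 95% v 80%: significant with probability 0.411, so non-significant with probability 1 − 0.411 = 0.589.
- Significant on complications and non-significant on success: 0.935 × 0.589 = 0.55 under independence. Under any dependence it lies between 0.935 + 0.589 − 1 = 0.52 and 0.59.
- Single example: 38/40 v 32/40 is an observed deficit of 15 points, with Fisher p = 0.087. The one-sided 95% upper Wald bound on the deficit is 0.15 + 1.645·√(0.95·0.05/40 + 0.80·0.20/40) = 26.8 points, far beyond the limit.

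**3. The same scenario with the limit tested and required.** The Farrington-Manning score test against 15 points at one-sided 5% passes a true 95% v 80% with probability 0.042. The two-part claim would then be made with probability 0.935 × 0.042 = 0.039, about 4%. The fall from 55% to 4% combines two changes, the test and the rule. A non-inferiority test reported without any rule would already miss the limit in 1 − 0.042, about 96%, of such trials.

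**4. Joint power when success is truly 95% in both arms, all 80 evaluable.**

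- Score test, one-sided 5%: non-inferiority power 0.819; joint 0.935 × 0.819 = 0.77 (0.75 to 0.82 under any dependence).
- Score test, one-sided 2.5%: 0.935 × 0.714 = 0.67.
- Score test, one-sided 5%, control complications 39.5%: 0.841 × 0.819 = 0.69.
- Wald bound, one-sided 5%: 0.935 × 0.921 = 0.86, but the Wald test passes a true 15-point deficit 7.1% of the time, above its nominal 5%.
- Agresti-Caffo bound, one-sided 5%: 0.935 × 0.872 = 0.82.

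Joint power is thus a property of the chosen method and alpha, and the plan gives neither.

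**The case against.** One primary outcome with a separately sized secondary outcome is a legitimate design, and no planned test becomes invalid because a joint rule is missing. Success is listed as its own aim, is reported in any case, and section 13 (Publication) commits to publishing negative and non-conclusive results. All of this stands. It is why the primary outcome should stay as it is, and why the point concerns analysis and wording. But reporting an outcome is not the same as saying which result would support a claim about it, and the planned Fisher test cannot show that success is maintained.

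Three stronger readings are tempting and are not supported:

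- *That the plan lets laparoscopy be declared better with success 15 points worse.* No section contains a rule declaring either approach better. Winning the primary comparison supports a statement about complications only. The 15 points are the plan's own limit, used here as an example, and not a loss that the plan permits.
- *That section 14 settles the trade-off in advance.* It says "Even so, we consider that lower complication would outweigh the risk of a subsequent treatment". This weighs the risk of a further treatment, in an ethical risk-benefit argument that also names lower success as the main disadvantage. It is not a rule for drawing conclusions.
- *That the 55% measures the missing rule alone.* It rests on the power of the difference test. The plan lacks both the right test and the rule, and the figure describes the two together.

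**Conclusion.** The point holds in this form: the plan hypothesises two results and sizes success as non-inferiority, but analyses success only for a difference and does not tie the two-part conclusion to its own limit. Followed as written, a true 95% v 80% deficit would be accompanied by significantly fewer complications and no significant difference in success in about 55% of trials. That figure assumes complications of 45% v 10%, 40 evaluable patients per arm and independence of the two outcomes.

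The planned 80 patients still give usable joint power: about 77% with the score test at one-sided 5%, less at one-sided 2.5% or with the lower external control rate. No single joint figure can be quoted without its method. The gap should be closed before results are known, while the reading of the two outcomes cannot be shaped by the data.

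**What to change.** Keep complications as the single primary outcome.

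- **Section 4, analysis.** Analyse complete ablation by a named non-inferiority method, for example a score confidence bound, against the 15-point limit. State the one-sided alpha (the plan's 54 implies 5%), do it in both the intention-to-treat and per-protocol sets, and say how a missing one-month CT is handled.
- **Section 4, conclusion.** Claim that laparoscopy reduces complications and maintains success only if the primary comparison is significant in its favour and non-inferiority is shown. Both must be met, so alpha is not split. If only complications pass, conclude only that complications are lower. Report success as not shown to be non-inferior, or as worse if it is significantly lower.
- **Sample size.** Give the joint power with its method and assumptions: about 77% (score test, one-sided 5%, all 80 evaluable, 45% v 10%), 67% at one-sided 2.5%, and about 69% at one-sided 5% if control complications are 39.5%. These figures leave no allowance for exclusions.

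The cost is wording in the protocol and SAP, with no added patients. The downside is that the full two-part conclusion becomes somewhat harder to reach than either part alone (93.5% and 81.9% at 40 per arm by the same methods).

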## Background

Surgically treated malignancies in the liver include primary liver cancers and liver metastases. Hepatocellular carcinoma (HCC) accounts for almost 90% of primary liver cancers, which is the sixth most common cancer worldwide and the fourth leading cause of cancer-related death globally. Furthermore, hematogenous spread of other cancers to the liver is very common due to the dual vascular supply, arising from both systemic arterial and portal venous systems. The most common primary site is colorectal cancer, however, depending on age and sex a wide range of primary cancers spread to the liver including breast, pancreatic, and neuroendocrine cancers. Patients with liver metastases have significantly reduced survival compared to those without liver metastases.

Many patients suffering from liver malignancies are not candidates for surgical interventions such as transplantation or hepatic resection due to extensive tumor burden, underlying liver disease, age, or other comorbidities. For some of these patients, ablation has proven to be a valuable alternative that is less invasive with fewer complication and with a shorter postprocedural hospital stay compared to resection. In addition, it preserves more of the liver parenchyma than resection which is especially important in patients with impaired liver function.

Ablation therapy is often guided by real-time ultrasound and can be performed either percutaneously, by laparoscopy or by laparotomy (open). Percutaneous ablation is the least invasive approach and is gold standard for the treatment of HCC and liver metastases when possible. However, some tumors may not be accessible percutaneously due to risk of injury to adjacent organs or due to insufficient visualization of the tumor. Ablation during open surgery allows treatment of tumors in locations difficult to reach percutaneously. At present, patients who cannot be treated percutaneously are offered open ablation in most centers. However, open surgery may be associated with a higher risk of complications which may be devastating for frail patients and patients with impaired liver function. More than 80% of patients diagnosed with HCC have preexisting cirrhosis, and these patients are at a higher risk of complications and have a higher postprocedural mortality due to the impaired liver function and portal hypertension. Therefore, a minimally invasive approach is considered especially relevant in these high-risk patients. Laparoscopic ablation is less invasive with a presumed lower complication rate than the open approach, however, offers some of the same advantages needed for tumors in locations not favorable for percutaneous ablation.

Success of the procedure is demonstrated by a complete ablation of the macroscopic tumor assessed by contrast-enhanced ultrasound or CT one month after procedure. Previous studies reported a complete ablation achieved in 94-100% of patients treated with ablation with no significant difference between percutaneous, laparoscopic, or open approach. However, no comparative study has been performed.

A study from our department found complications in 45% of open ablations based on the Clavien Dindo Classification which was comparable to that of patients undergoing liver resection. An external study found comparable results of 39.5%. In contrast, the complication rate after

percutaneous ablation is as low as 5% and the literature suggests that laparoscopic approach have similar low complication rates.

### Previous studies

No previous randomized studies or even comparative studies have been carried out investigating this subject. The literature consists of few smaller reports of case series. These reports support that laparoscopic ablation is both safe and efficient.

## 3. Method

The study is a randomized, controlled, multicenter study in patients with liver malignancies treated at the four Danish liver surgery centers (Rigshospitalet, Odense, Århus and Aalborg). Patients with one or more liver tumor suitable for ablation as primary treatment, but not amenable for percutaneous ablation will be randomized between laparoscopic and open ablation. Opaque envelopes with patient numbers containing the randomization sequence will be opened after informed consent has been obtained. We plan to include 80 patients with 40 patients per arm. Patients will be randomized 1:1 (see below). Randomization will be stratified on center level to ensure comparable populations between the groups within each center.

Due to perioperative findings, the treatment to which the patient is randomized to may be considered not feasible or inappropriate, e.g. due to insufficient visualisation of tumor or findings that warrant a different treatment strategy. In these cases, the treatment strategy is based on the surgeons preferences. In laparoscopic cases, a minimally invasive approach should be maintained if possible, e.g. by combining laparoscopy with percutaneous ablation needle placement.

Ninety days after the procedure, the patient chart will be evaluated to register patient characteristics and outcomes. Moreover, at one month all patients will receive a CT-scan to evaluate success rate (complete ablation response). The CT-scan is part of standard of care, it is assessed by an experienced radiologist, and it is not part of this study. Before surgery and one month after, health related quality of life (HRQoL), the psychological burden and level of recovery will be assessed. Open ablation is standard of care. Thus, the intervention group will receive a treatment with assumed fewer complications and similar success rate.

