## 12. Recruitment of subjects and informed consent

The participants are among the patients who are already referred for treatment of a liver tumor at the included centers. These patients are identified by a clinician, and informed about the possibility of being informed about the project.

After a joint decision between a specialist and the patient about ablation of a liver tumor not amenable for percutaneous ablation, typically at the first visit to the surgical outpatient clinic, and after it has been ensured that the inclusion and exclusion criteria are met, the patient will be oriented about the project and offered written and oral information.

Interested patients are informed orally and given written participant information. The patient will be offered an in-depth interview during the day. During the interview, the patient will receive verbally sufficient information about the purpose and structure of the study, as well as potential risks and disadvantages. The patients will be informed that participation is voluntary and that they can withdraw from the study at any time, without this having an impact on their further progress in the department. They will also be informed that they may be withdrawn from the study at the discretion of the investigator responsible for the study.

The patients will also be informed about the treatment they will be offered if they choose to say no to participating, and they will also be informed that all data will be treated confidentially.

A copy of the information and signed declaration of consent will be given to the patient and a copy will be kept in the medical record. Current regulations from the Scientific Ethics Committee regarding informed consent will be followed.

It is the responsibility of the primary investigator that all patients receive oral information, so that it is ensured that the patient is completely aware of all aspects of participation in the study. The patient can withdraw his consent to participate in the study at any time. If the patient decides to do this, it will not impair his or her relationship with investigators or other staff, and the patient will continue to receive the best treatment the department can offer.

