The conversation with the patient will be handled by the investigator, or a person with delegated responsibility for this, when the patient accepts ablation as treatment in the outpatient clinic, and will take place in a calm environment and with the possibility for the patient and any relatives can ask questions. By written summons, the patient is invited to have a relative with him/her on the day of the outpatient interview.

The patient can give informed consent immediately at the outpatient interview, where the decision on ablation as treatment and project information have taken place. Alternatively, the patient can be offered a new interview after a few days of reflection. Longer reflection time will not be appropriate for the patient's treatment, as this could delay the time to surgery. If the patient so wishes, he/she will be offered time to think before giving consent until the morning of the operation day.

When it is ensured that the patient has understood the information given, had the desired time to think, and has received answers to any questions, informed consent is sought.

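### No latest time is set for opening the randomisation envelope, so the plan permits the arm to be known for an unstated interval before surgery

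*Combined protocol and SAP*

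**What the plan says.** Section 3 (Method) sets the rule: "Opaque envelopes with patient numbers containing the randomization sequence will be opened after informed consent has been obtained". It names no later time point and does not tie opening to the operating day.

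Section 12 (Recruitment of subjects and informed consent) gives a wide window for consent. At the early end, "The patient can give informed consent immediately at the outpatient interview". At the late end, a patient who wishes it "he/she will be offered time to think before giving consent until the morning of the operation day". The same section discourages a long delay: "Longer reflection time will not be appropriate for the patient's treatment, as this could delay the time to surgery". That sentence implies that surgery falls on a later day than the interview, but no interval is given.

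On leaving the trial, section 12 says "The patient can withdraw his consent to participate in the study at any time" and that patients are told "they may be withdrawn from the study at the discretion of the investigator responsible for the study". No criteria are given for the second route.

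The primary outcome is counted over 30 days from ablation (section 3, Primary outcome). Section 4 plans intention-to-treat and per-protocol analyses without defining either, and has no rule for withdrawals or missing outcomes. No blinding is described.

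**The concern.** A surgical trial without blinding is exposed to selective loss between allocation and operation, and the length of that interval is under the designers' control. Here the plan leaves it open. A patient who consents in clinic may learn the arm then, and so may the surgeon. Either can then act on that knowledge, the patient by withdrawing and the investigator by using the discretionary withdrawal.

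The protocol also favours one arm in its own account. Of laparoscopy, section 14 says "All side effects should be less severe compared with standard of care". If patients hear something similar, disappointment would fall mainly on the open arm.

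Cancelled operations and changes of plan in the same interval also become post-randomisation events, although they need not. What is at stake is the comparability of the two randomised groups for the primary outcome. Extra recruitment does not restore comparability once losses depend on the arm.

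**Working it through.** **1. What the timing rules permit.** Earliest opening is at the outpatient interview, straight after consent. Latest is the operation morning or after. Both comply with section 3. The interval at risk therefore runs from zero to the full wait for surgery, and the documents give no figure for that wait.

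**2. Which patients are lost.**
- Full withdrawal of consent before surgery: no rule says that chart data may still be used, so the outcome may be lost.
- No operation: a 30-day outcome counted from ablation has no start date.
- Change of procedure without withdrawal: there is an operation and a chart-based outcome (section 8), and intention to treat keeps the patient in the assigned arm.

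Only the first two are losses.

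**3. The plan's own sample size.** Inputs from section 4 (Sample size): 45% v 10%, alpha 5%, power 80%. Two-sided, pooled variance, mean rate 0.275:
- n = [1.960 × √(2 × 0.275 × 0.725) + 0.842 × √(0.45 × 0.55 + 0.10 × 0.90)]² / 0.35² = 24.3 per arm
- with continuity correction: n/4 × [1 + √(1 + 4/(n × 0.35))]² = 29.8, so 30 per arm, 60 in total

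This matches the plan. The 80 planned patients leave a margin of 20.

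**4. Power if only the open arm loses patients** (exact two-sided Fisher, 45% v 10%):

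| Open v laparoscopic | Power |
|---|---|
| 40 v 40 | 93% |
| 36 v 40 | 93% |
| 32 v 40 | 91% |
| 30 v 30 | 83% |

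Loss of power is not the problem.

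**5. Bias.** Let a share w of the open arm leave, with complication risk r (both assumed). The rate among those who stay is (0.45 − w·r)/(1 − w).
- w = 10%: 47.2% if r = 25%; 42.8% if r = 65%
- w = 20%: 50.0% if r = 25%; 40.0% if r = 65%

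The shift is 2 to 5 points, and its direction depends on who leaves.

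**6. Can four open-arm losses change the conclusion?** Four is 10% of one arm (assumed). Two-sided Fisher p-values, laparoscopic v open:

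| Scenario | No loss | Four leave |
|---|---|---|
| Planned rates, leavers without complications | 4/40 v 18/40: 0.0009 | 4/40 v 18/36: 0.0001 |
| Planned rates, leavers with complications | 4/40 v 18/40: 0.0009 | 4/40 v 14/36: 0.006 |
| Smaller difference, leavers without complications | 8/40 v 17/40: 0.053 | 8/40 v 17/36: 0.015 |
| Smaller difference, leavers with complications | 8/40 v 18/40: 0.031 | 8/40 v 14/36: 0.082 |

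The last two rows were chosen to lie near 0.05 and assume that all four leavers are of one kind. If leaving were unrelated to outcome, the chance that four leavers from 17/40 are all complication-free is C(23,4)/C(40,4) = 8,855/91,390, about 10%. These rows show what is possible and are not a forecast.

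**The case against.** The other side has a good deal of force. After consent is a lower bound: a centre that opens envelopes on the operating day already complies. A reader might infer that envelopes will be opened in the clinic, well before surgery. The documents say neither, and the short reflection period in section 12 suggests that the wait is not meant to be long.

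A reader might also infer that every patient who leaves takes the outcome with them. That is too strong, for the reason in step 2: outcomes come from charts, the one-month CT is standard care, and intention to treat is planned.

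The incentive to leave the open arm is uncertain too. Open ablation is standard care, and nothing says that a patient who leaves would get laparoscopy outside the trial; leaving may simply lead back to open ablation. The favourable account of laparoscopy is in the ethics section, and the patient information is not available for review.

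Finally, 80 patients against 60 needed covers a modest loss.

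All of this limits the size of the concern. It does not remove the gap: the plan allows early opening, gives no reason for it, and has no rule for those who withdraw between opening and surgery.

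**Conclusion.** The concern holds as a gap in the allocation procedure. The plan permits the arm to be known to patient and surgeon for an unstated interval before surgery, and full withdrawals or cancelled operations in that interval are losses made with knowledge of the arm.

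The documents do not support saying that the open arm will become self-selected, that the bias will favour laparoscopy, or that the trial will be underpowered. No loss rate, interval or risk among leavers is given, so neither size nor direction can be derived. On the assumed loss of four open-arm patients, the conclusion at the planned rates does not change (p at or below 0.006). At differences of roughly 20% v 43–45% it can change in either direction. The reason to act is that this loss is avoidable and the remedy is inexpensive.

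**What to change.** In section 3 (Method), replace the sentence on envelopes with a rule such as: the envelope is opened on the day of surgery, at the earliest the working day before, after consent has been obtained, eligibility confirmed, baseline questionnaires completed and the operation confirmed to go ahead. Completing the questionnaires first also keeps knowledge of the arm out of the baseline answers.

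In section 4, define intention to treat as all patients randomised from that point, in the assigned arm. Patients who leave earlier are not randomised and do not enter the analysis. Late opening shortens the interval but does not settle what happens to later withdrawals. It would help to report these by arm with reasons, and to ask at consent for permission to keep collecting the 30-day outcome from the chart.

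The cost in text is a few sentences. The practical cost is that theatre lists at all four centres must be able to run either approach until the envelope is opened. The plan already accepts this for patients who consent on the operation morning, but that is an option for those who ask for it, and it would now apply to everyone. The working-day-before allowance gives some room for planning.
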